8.1.2 Serious Adverse Event Definition

Serious AE (SAE) means any untoward medical occurrence that at any dose:

- Results in **death**.
- Is **life-threatening** (refers to an AE in which the patient was at risk of death at the time of the event. It does not refer to an event which hypothetically might have caused death if it were more severe).
- Requires inpatient **hospitalization or prolongation of an existing hospitalization** (see clarification in the paragraph below on planned hospitalizations).
- Results in **persistent or significant disability or incapacity**. (Disability is defined as a substantial disruption of a person's ability to conduct normal life functions).
- Is a **congenital anomaly/birth defect**.
- Is a **medically important event**. This refers to an AE that may not result in death, be immediately life threatening, or require hospitalization, but may be considered serious when, based on appropriate medical judgment, may jeopardize the patient, require medical or surgical intervention to prevent 1 of the outcomes listed above, or involves suspected transmission via a medicinal product of an infectious agent. Examples of such medical events include allergic bronchospasm requiring intensive treatment in an emergency room or at home, blood dyscrasias or convulsions that do not result in inpatient hospitalization, or the development of drug dependency or drug abuse; any organism, virus, or infectious particle (eg, prion protein transmitting Transmissible Spongiform Encephalopathy), pathogenic or nonpathogenic, is considered an infectious agent.
- New primary malignancy (reportable for 3 years)

Clarification should be made between a serious AE (SAE) and an AE that is considered severe in intensity (Grade 3 or 4), because the terms serious and severe are NOT synonymous. The general term *severe* is often used to describe the intensity (severity) of a specific event; the event itself, however, may be of relatively minor medical significance (such as a Grade 3 headache). This is NOT the same as

serious, which is based on patient/event outcome or action criteria described above, and is usually associated with events that pose a threat to a patient's life or ability to function. A severe AE (Grade 3 or 4) does not necessarily need to be considered serious. For example, a white blood cell count of 1000/mm³ to less than 2000 is considered Grade 3 (severe) but may not be considered serious. Seriousness (not intensity) serves as a guide for defining regulatory reporting obligations.

8.2 Procedures for Reporting Serious Adverse Events

AEs may be spontaneously reported by the patient and/or in response to an open question from study personnel or revealed by observation, physical examination, or other diagnostic procedures. Any clinically relevant deterioration in laboratory assessments or other clinical finding is considered an AE. When possible, signs and symptoms indicating a common underlying pathology should be noted as one comprehensive event. For serious AEs, the investigator must determine both the intensity of the event and the relationship of the event to study drug administration.

AEs which are serious must be reported to Millennium Pharmacovigilance (or designee) from the first dose of study drug through 30 days after administration of the last dose of ixazomib. Any SAE that occurs at any time after completion of ixazomib treatment or after the designated follow-up period that the sponsor-investigator and/or sub-investigator considers to be related to any study drug must be reported to Millennium Pharmacovigilance (or designee). In addition, new primary malignancies that occur during the follow-up periods must be reported, regardless of causality to study regimen, for a minimum of three years after the last dose of the investigational product, starting from the first dose of study drug. All new cases of primary malignancy must be reported to Millennium Pharmacovigilance (or designee).

Planned hospital admissions or surgical procedures for an illness or disease that existed before the patient was enrolled in the trial are not to be considered AEs unless the condition deteriorated in an unexpected manner during the trial (e.g., surgery was performed earlier or later than planned). All SAEs should be monitored until they are resolved or are clearly determined to be due to a patient's stable or chronic condition or intercurrent illness(es).

Since this is an investigator-initiated study, the principal investigator [name], also referred to as the sponsor-investigator, is responsible for reporting serious adverse events (SAEs) to any regulatory agency and to the sponsor- investigator's EC or IRB.

Regardless of expectedness or causality, all SAEs must also be reported in English to Millennium Pharmacovigilance (or designee):

Fatal and Life Threatening SAEs within 24 hours of the sponsor-investigator's observation or awareness of the event

All other serious (non-fatal/non life threatening) events within 4 calendar days of the sponsor-investigator's observation or awareness of the event

See below for contact information for the reporting of SAEs to Millennium Pharmacovigilance.

The sponsor-investigator must fax or email the SAE Form per the timelines above. A sample of an SAE Form will be provided.

The SAE report must include at minimum:

- **Event term(s)**
- **Serious criteria**
- **Intensity of the event(s):** Sponsor-investigator's or sub-investigator's determination. Intensity for each SAE, including any lab abnormalities, will be determined by using the NCI CTCAE version 4 as a guideline, whenever possible. The criteria are available online at <http://ctep.cancer.gov/reporting/ctc.html>.
- **Causality of the event(s):** Sponsor-investigator's or sub-investigator's determination of the relationship of the event(s) to study drug administration.

Follow-up information on the SAE may be requested by Millennium.

Intensity for each SAE, including any lab abnormalities, will be determined by using the NCI CTCAE version 4, as a guideline, whenever possible. The criteria are available online at <http://ctep.cancer.gov/reporting/ctc.html>.

In the event that this is a multisite study, the sponsor-investigator is responsible to ensure that the SAE reports are sent to Millennium Pharmacovigilance (or designee) from all sites participating in the study. Sub-investigators must report all SAEs to the sponsor-investigator so that the sponsor-investigator can meet his/her foregoing reporting obligations to the required regulatory agencies and to Millennium Pharmacovigilance, unless otherwise agreed between the sponsor-investigator and sub-investigator(s).

Relationship to all study drugs for each SAE will be determined by the investigator or sub-investigator by responding yes or no to the question: Is there a reasonable possibility that the AE is associated with the study drug(s)?

Sponsor-investigator must also provide Millennium Pharmacovigilance with a copy of all communications with applicable regulatory authorities related to the study product(s), as soon as possible but no later than 4 calendar days of such communication.

8.3 Procedures for Reporting Drug Exposure During Pregnancy and Birth Events

If a woman becomes pregnant or suspects that she is pregnant while participating in this study or within 90 days after the last dose, she must inform the investigator immediately and permanently discontinue all study drugs. The sponsor-investigator must immediately fax a completed Pregnancy Form to the Millennium Department of Pharmacovigilance or designee (see Section 8.2). The pregnancy must be followed for the final pregnancy outcome.

If a female partner of a male patient becomes pregnant during the male patient's participation in this study, the sponsor-investigator must also immediately fax a completed Pregnancy Form to the

Millennium Department of Pharmacovigilance or designee (see Section 8.2). Every effort should be made to follow the pregnancy for the final pregnancy outcome.

Suggested Pregnancy Reporting Form:

- Pregnancy Report Form (provided by Millennium)

11. APPENDICES

11.1 Eastern Cooperative Oncology Group (ECOG) Scale for Performance Status

Grade	Description
0	Normal activity. Fully active, able to carry on all predisease performance without restriction
1	Symptoms but ambulatory. Restricted in physically strenuous activity, but ambulatory and able to carry out work of a light or sedentary nature (eg, light housework, office work)
2	In bed < 50% of the time. Ambulatory and capable of all self-care, but unable to carry out any work activities. Up and about more than 50% of waking hours.
3	In bed > 50% of the time. Capable of only limited self-care, confined to bed or chair more than 50% of waking hours.
4	100% bedridden. Completely disabled. Cannot carry on any self-care. Totally confined to bed or chair
5	Dead

Source: Oken MM, Creech RH, Tormey DC, Horton J, Davis TE, McFadden ET et al. Toxicity and response criteria of the Eastern Cooperative Oncology Group. *Am J Clin Oncol* 1982; 5 (6):649-55.

11.2 Cockcroft-Gault Equation

For males:

$$\text{Creatinine Clearance} = \frac{(140 - \text{age}[\text{years}]) \times \text{weight} [\text{kg}]}{72 \times (\text{serum creatinine}[\text{mg/dL}])} \quad \text{OR} \quad \frac{(140 - \text{age}[\text{years}]) \times \text{weight} [\text{kg}]}{0.81 \times (\text{serum creatinine}[\mu\text{mol/L}])}$$

For females:

$$\text{Creatinine Clearance} = \frac{0.85 (140 - \text{age}[\text{years}]) \times \text{weight} [\text{kg}]}{72 \times (\text{serum creatinine}[\text{mg/dL}])} \quad \text{OR} \quad \frac{0.85 (140 - \text{age}[\text{years}]) \times \text{weight} [\text{kg}]}{0.81 \times (\text{serum creatinine}[\mu\text{mol/L}])}$$

Source: Cockcroft DW, Gault MH. Prediction of creatinine clearance from serum creatinine. *Nephron* 1976;16(1):31-41.

11.4 IMWG Response Criteria

Adapted from International Myeloma Working Group uniform response criteria¹ and Kyle and Rajkumar².

Stringent Complete Response (sCR)

CR as defined below plus

Normal FLC ratio and

Absence of clonal cells in bone marrow by immunohistochemistry or immunofluorescence¹

Complete Response² (CR)

Negative immunofixation on the serum and urine and

Disappearance of any soft tissue plasmacytomas and

<5% plasma cells in bone marrow³

Very Good Partial Response (VGPR)

Serum and urine M-protein detectable by immunofixation but not on electrophoresis or 90% reduction in serum M-protein plus urine M-protein <100mg per 24 hour

Partial Response⁴ (PR)

≥ 50% reduction of serum M-protein and reduction in 24 hour urinary M protein by ≥ 90% or to <200mg per 24 hour

If the serum and urine M protein are unmeasurable⁵, a ≥ 50% decrease in the difference between involved and uninvolved FLC levels is required in place of the M-protein criteria. If serum and urine M-protein are

¹ Confirmation with repeat bone marrow biopsy not needed

² Note clarification to IMWG criteria for coding CR and VGPR in patients in whom the only measurable disease is by serum FLC levels: CR in such patient is defined as a normal FLC ratio of 0.26-1.65 in addition to CR criteria listed above. VGPR in such patients is defined as a >90% decrease in the difference between involved and uninvolved FLC levels.

³ Confirmation with repeat bone marrow biopsy not needed

⁴ Confirmation with repeat bone marrow biopsy not needed

⁵ In order to apply definition, patient must have measurable disease defined by at least one of the following:

- Serum M-protein ≥ 1g/dl
- Urine M-protein ≥200mg/24hour
- Serum FLC assay : Involved FLC level ≥ 10mg/dl provided serum FLC ratio is abnormal Bone marrow plasma cells ≥ 30%

unmeasurable, and serum free light assay is also unmeasurable, $\geq 50\%$ reduction in plasma cells is required in place of M-protein, provided baseline bone marrow plasma cell percentage was $\geq 30\%$

In addition to the above listed criteria, if present at baseline, a $\geq 50\%$ reduction in the size of soft tissue plasmacytomas is also required.

Minor Response (MR)

$\geq 25\%$ but $< 49\%$ reduction of serum M protein and reduction in 24 hr. M protein by 50-89%, which still exceeds 200mg per 24hr

In addition to the above criteria, if present as baseline, 25-49% reduction in the size of soft tissue plasmacytomas is also required.

No increase in size or number of lytic bone lesions (development of compression fracture does not exclude response)

Stable disease (SD)

Not meeting criteria for MR, CR, VGPR, PR or progressive disease

Progressive Disease⁶ (PD)

Any one or more of the following:

Increase of $\geq 25\%$ from lowest response level in Serum M component and/or (the absolute increase must be $\geq 0.5\text{g/dL}$)⁷.

Urine M-component and/or (the absolute increase must be $\geq 200\text{mg}/24$ hour.

Only in patients without measurable serum and urine M-protein levels: the difference between involved and uninvolved FLC levels. The absolute increase must be $>100\text{mg/l}$.

Bone marrow plasma cell percentage: the absolute % must be $\geq 10\%$ ⁸.

Definite development of new bone lesions or soft tissue plasmacytomas or definite increase in the size of existing bone lesions or soft tissue plasmacytomas.

Development of hypercalcemia (corrected serum calcium $> 2.65\text{mmol/l}$) that can be attributed solely to the plasma cell proliferative disorder.

NOTE: The IMWG uniform response criteria have clarified that patients in CR need to meet the same criteria for disease progression as other patients not in CR for purposes of calculating progression-free survival and time to progression.

All response categories (CR, sCR, VGPR and PR) require two consecutive assessments made at any time before the institution of any new therapy; complete, PR and SD categories also require no known evidence of progressive or new bone lesions if radiographic studies were performed. Radiographic studies are not required to satisfy these response requirements. Bone marrow assessments need not be confirmed.

⁶ All relapse categories require two consecutive assessments made at any time before classification as relapse or disease progression and/or the institution of any new therapy

⁷ For progressive disease, serum M component increases of $\geq 1\text{gm/dl}$ are sufficient to define relapse if starting M-component is $\geq 5\text{g/dl}$

⁸ Relapse from CR has the 5% cut-off versus 10% for other categories of relapse

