7.1.6 Efficacy Analysis

The primary efficacy objective is to determine the overall response rate to treatment with ITD combination therapy in RRMM patients. Overall response is defined as achievement of a PR or better

(PR, VGPR, CR or sCR) as defined by the IMWG criteria (Appendix 4). The overall response rate (ORR) will be calculated as the number of patients who have experienced at least a partial response, divided by the number of patients registered on the trial. Patients who withdraw from the study prior to re-staging, or who are lost to follow-up before re-staging and are not known to have achieved at least a PR, or whose re-staging information is missing for any reason, will be considered to have not met the primary efficacy endpoint.

The primary efficacy analysis will be based on the calculation of the observed ORR and its posterior probability distribution. Evidence of efficacy of the ITD combination therapy will be based on two PoC criteria:

1. Observed ORR \geq 60%
2. Posterior probability that the true ORR exceeds 45% is $>$ 90% (given the observed data)

In addition, the percentiles of the posterior probability distribution for ORR, in particular the 95% uncertainty interval, defined by the 2.5 and 97.5 percentiles and also the posterior probability that the true ORR exceeds 45%, will be reported. The analysis will use a minimally informative prior distribution for the ORR, namely, Beta($a=0.86805$, $b=1$) for which the median ORR is 45% and the amount of prior information is equivalent to approximately 1.87 ($=a+b$) patients.

If an interim analysis of ORR is required for any reason (e.g. a review of efficacy by the TMC or sponsor), the posterior probability distribution will be updated, using the minimally informative prior distribution and the accumulated data, and reported as appropriate.

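### The PR rule in Appendix 11.4 gives no route of its own to patients whose only measurable M-protein is urinary, although footnote 5 accepts them as assessable

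*Protocol*

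**What the plan says.** Section 7.1.6 of the Protocol counts PR, VGPR, CR and sCR as overall response, refers to the IMWG appendix for their definitions, and computes ORR as "the number of patients who have experienced at least a partial response, divided by the number of patients registered on the trial".

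Appendix 11.4 then sets the rules:

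- **PR, main clause:** "≥ 50% reduction of serum M-protein and reduction in 24 hour urinary M protein by ≥ 90% or to <200mg per 24 hour". The serum and urine conditions are joined by an *and*.
- **PR, replacement:** "If the serum and urine M protein are unmeasurable⁵, a ≥ 50% decrease in the difference between involved and uninvolved FLC levels is required". A further replacement, by marrow plasma cells, applies when the free light chain (FLC) assay is unmeasurable too.
- **Footnote 5, on who can be assessed:** "In order to apply definition, patient must have measurable disease defined by at least one of the following". The list contains serum M-protein of at least 1 g/dL, "Urine M-protein ≥200mg/24hour", FLC and marrow.
- **VGPR:** either "Serum and urine M-protein detectable by immunofixation but not on electrophoresis", or a 90% serum reduction together with urine below 100 mg/24 h.
- **CR:** begins with "Negative immunofixation on the serum and urine and" and adds plasmacytoma and marrow conditions. It asks for no percentage fall.

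Inclusion criterion 4 in section 5.1 asks for relapsed/refractory myeloma and 1 to 3 prior therapies, with no measurability requirement. Urine-only patients can therefore be registered.

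**The concern.** Footnote 5 names four ways to be measurable, and the PR rule provides for three of them. A serum-only patient satisfies the urine condition through its absolute limit. FLC-only and marrow-only patients each have a written replacement. A urine-only patient has neither: the serum condition carries no absolute alternative, and the FLC replacement is closed because urine is measurable.

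This rule decides the primary endpoint. The denominator is all registered patients, so a urinary responder who is not credited with PR counts as a failure, and under a literal reading the error runs only against ITD. Duration of response (7.1.6) starts at overall response and would lose the same patients. Sites in an open-label, multi-centre trial could also score identical records differently, some following the text and some judging the urine alone.

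**Working it through.** **Step 1: apply the text to records.** The values are illustrative. The limits are those of Appendix 11.4.

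| Record | Serum M-protein (g/dL) | Urine M-protein (mg/24 h) | Serum condition | Urine condition | PR as written |
|---|---|---|---|---|---|
| A, serum-measurable | 2.0 to 0.8 (60% fall) | 50 to 40 | met | met (below 200) | yes |
| B, urine-only, no serum | 0 to 0 | 2,000 to 150 (92.5% fall) | undefined (0/0) | met | cannot be credited |
| C, urine-only, small serum | 0.3 to 0.2 (33% fall) | 2,000 to 150 (92.5% fall) | not met | met | no |
| D, urine-only, small serum | 0.3 to 0.15 (50% fall) | 2,000 to 150 (92.5% fall) | met | met | yes |

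C and D have the same urinary response. They differ by 0.05 g/dL in a component that footnote 5 treats as unmeasurable. B and C do not reach the 90%-reduction arm of VGPR either, because it needs a serum percentage fall and urine below 100 mg. If the urine protein still shows on electrophoresis, the other VGPR alternative and CR are closed too.

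**Step 2: reproduce the plan's figure.** Inputs from sections 7.1.1 and 7.1.6: n = 45, true ORR 65%, prior Beta(0.86805, 1), and success if the observed ORR is at least 60% and the posterior probability of ORR above 45% exceeds 90%.

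- 0.60 × 45 = 27 responders.
- With x = 27 the posterior is Beta(27.868, 19), and P(ORR > 0.45) = 0.977. The second criterion is met, so 27 is the threshold.
- P(X ≥ 27) for Binomial(45, 0.65) = 0.806. The stated 0.80 is reproduced.

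**Step 3: size of a possible loss.** The protocol gives no urine-only share. The assumption is that k = 1 to 5 of 45 patients are affected (1/45 = 2.2% to 5/45 = 11.1%), with a true ORR of 65% in every group.

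- *None can count:* P(X ≥ 27) with X ~ Binomial(45 − k, 0.65).
- *Half of their responders still count* (through CR, VGPR or a serum fall; an assumption): P(X + Y ≥ 27) with Y ~ Binomial(k, 0.65 × 0.5 = 0.325), independent of X.

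| k | None can count | Half of responders count |
|---|---|---|
| 0 | 0.81 | 0.81 |
| 1 | 0.75 | 0.78 |
| 2 | 0.68 | 0.75 |
| 3 | 0.61 | 0.71 |
| 4 | 0.53 | 0.68 |
| 5 | 0.44 | 0.64 |

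If such patients are in practice scored on urine alone, nobody is lost and the figure stays at 0.81.

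**The case against.** A reader might infer that every urine-only patient is a certain failure in the primary ORR, or that the trial is underpowered. The documents support neither.

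- **Other routes stay open.** CR and sCR need no percentage fall in serum, and the first VGPR alternative is arguably available as well. All of them count in ORR. This stands, and the column in which none can count is therefore a worst case.
- **PR is not always out of reach.** Unmeasurable serum means below 1 g/dL, not zero, so a small component can halve, as in record D. This stands too. The bar is strict only where there is no serum M-protein, and there the text leaves 0/0 undefined rather than declaring it failed. Below 1 g/dL the difficulty changes character: the endpoint then turns on an unreliable quantity.
- **Footnote 5 shows that these patients were meant to be assessable,** so a sensible assessor would use the urine. That is probably the intention, but the PR clause does not say so. The two parts of the appendix conflict, and the conflict is in the endpoint definition.
- **The SAP might settle the coding.** It may, and it is not available here. But 7.1.6 defines response by this appendix, which already spells out replacements for the other measurable classes. A SAP rule for this class would have to override the written PR condition.
- **The share is assumed.** Correct. The table shows sensitivity and estimates nothing about this trial.

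**Conclusion.** The gap is real but limited. Appendix 11.4 requires a percentage fall in serum M-protein for PR, and for the 90%-reduction arm of VGPR. For PR it lifts that requirement only when serum and urine are both unmeasurable, while footnote 5 accepts urine alone. Urine-only is the one measurable class left without a PR route of its own.

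The effect on ORR cannot be determined from the protocol. Under the assumed 1 to 5 affected patients, the probability of reaching 27 of 45 lies between 0.75 and 0.44 in the worst case, between 0.78 and 0.64 if half of such responders count, and at 0.81 if urine is used in practice. The sample size and the stated power are sound. Because success rests on a count of 27, one or two records scored differently could decide the result, so the rule should be settled before responses are derived.

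**What to change.** Add to Appendix 11.4: where baseline serum M-protein is below 1 g/dL and baseline urine M-protein is at least 200 mg/24 h, the serum percentage condition of PR and VGPR does not apply, and response is judged on the urine condition, provided the serum component does not meet the criteria for progression.

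Leave the rest unchanged, including the FLC and marrow replacements. In particular, do not go further and drop the urine condition whenever baseline urine is below 200 mg/24 h. That would loosen limits that are not at fault: a serum-measurable patient with a 90% serum fall and urine steady at 150 mg/24 h would become VGPR despite the limit of 100 mg/24 h.

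The cost is one statement in the appendix and the matching line in the response derivation. No new tests, visits or patients are needed.

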Skeletal Survey ^f	X				X		
Assessment of EMD if clinically indicated ^g	X				X		
B ₂ M	X	X					
LDH	X	X				X	
SPEP	X	X				X	
UPEP ^h	X	X				X	

FLC	X	X				X	
CFNA ⁱ		X		X	X	X	
BMAT ^j	X				X	X	
New primary malignancy assessment ^k		X				X	X
AE reporting	X	X				X	X
Progression data ^l							X

Abbreviations:

CR = complete response; EOT = end of treatment; FISH = fluorescent in-situ hybridization; ECOG = Eastern Cooperative Oncology Group; ECG = electrocardiogram; FBE = full blood examination; QOL = quality of life; EMD = extramedullary disease; B₂M = beta 2 microglobulin; LDH = lactate dehydrogenase; SPEP = serum protein electrophoresis; UPEP = urine protein electrophoresis; FLC = free light chain assay; CFNA = circulating free nucleic acid; BMAT = bone marrow aspirate and trephine; AE = adverse event.

^a Screening should be conducted within 28 days of starting treatment.

^b Day 15 evaluations only for cycles 1 to 3.

^c Patients who discontinue the study drug regimen for disease progression must complete the end-of-treatment (EOT) visit, which should occur within 30 days (\pm 1 week) after the last dose of study drug and before the start of subsequent antineoplastic therapy.

^d A serum pregnancy test will be performed for women of childbearing potential during screening, day 1 of each cycle and at EOT. The serum pregnancy test may be collected up to 3 days before dosing. The results must be available and negative before the study drug regimen is administered.

^e QLQ-C30 = Quality of Life Questionnaire.

^f Within 60 days of cycle 1 day 1 acceptable at screening. To be repeated at time of serological CR and otherwise only if clinically indicated.

^g For those with documented extramedullary disease, radiographic assessments should be undertaken at screening, at the time of serological CR and otherwise, only if clinically indicated. The same imaging modality used at screening (CT/PET-CT/MRI) should be used for all follow-up assessments.

^h Only to be repeated if abnormal at baseline.

ⁱ Correlative studies (peripheral blood collection)

^j BMAT will be obtained at screening, at serological CR and progression for response assessment and correlative studies.

^k New primary malignancies that occur during the follow-up period must be reported, regardless of causality to study regimen, for a minimum of three years after the last dose of the investigational product

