5. STUDY POPULATION

5.1 Inclusion Criteria

Each patient must meet all of the following inclusion criteria to be enrolled in the study:

1. Male or female patients 18 years or older.
2. Voluntary written consent must be given before performance of any study related procedure not part of standard medical care, with the understanding that consent may be withdrawn by the patient at any time without prejudice to future medical care.

3. Female patients who:

- Are postmenopausal for at least 1 year before the screening visit, OR
- Are surgically sterile, OR
- If they are of childbearing potential, agree to practice 2 effective methods of contraception, at the same time, from the time of signing the informed consent form through 90 days after the last dose of study drug, OR
- Agree to practice true abstinence when this is in line with the preferred and usual lifestyle of the subject. (Periodic abstinence [eg, calendar, ovulation, symptothermal, post-ovulation methods] and withdrawal are not acceptable methods of contraception.)

Male patients, even if surgically sterilized (ie, status post-vasectomy), must agree to one of the following:

- Agree to practice effective barrier contraception during the entire study treatment period and through 90 days after the last dose of study drug, OR
- Agree to practice true abstinence when this is in line with the preferred and usual lifestyle of the subject. (Periodic abstinence (eg, calendar, ovulation, symptothermal, post-ovulation methods] and withdrawal are not acceptable methods of contraception.)

4. Patients must have a diagnosis of a relapsed/refractory multiple myeloma and have had between 1-3 prior therapies

5. Eastern Cooperative Oncology Group (ECOG) performance status 0, 1, or 2 (See appendix 11.1).

6. Patients must meet the following clinical laboratory criteria:

- Absolute neutrophil count (ANC) $\geq 1,000/\text{mm}^3$ and platelet count $\geq 75,000/\text{mm}^3$. Platelet transfusions to help patients meet eligibility criteria are not allowed within 3 days before study enrollment.
- Total bilirubin $\leq 1.5 \times$ the upper limit of the normal range (ULN).
- Alanine aminotransferase (ALT) and aspartate aminotransferase (AST) $\leq 3 \times$ ULN.
- Calculated creatinine clearance ≥ 30 mL/min (see Appendix 11.3).

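### Appendix 11.4 scores partial response by a marrow plasma-cell fall in marrow-only patients, but no on-treatment marrow is scheduled short of serological CR, so such patients will tend to count as non-responders

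*Protocol*

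**What the plan says.** **Response definition.** Footnote 5 of protocol Appendix 11.4 begins "In order to apply definition, patient must have measurable disease defined by at least one of the following" and lists four routes: serum M-protein, urine M-protein, involved FLC with an abnormal ratio, and bone marrow plasma cells of at least 30%. If the first three are all unmeasurable, the Partial Response text says a 50% or greater "reduction in plasma cells is required in place of M-protein, provided baseline bone marrow plasma cell percentage was" at least 30%.

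**Eligibility.** The disease criterion in section 5.1 is "Patients must have a diagnosis of a relapsed/refractory multiple myeloma and have had between 1-3 prior therapies". Measurable disease is not required by any route.

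**Marrow schedule.** The footnote to the Schedule of Events says "BMAT will be obtained at screening, at serological CR and progression for response assessment and correlative studies". The grid marks bone marrow aspirate and trephine (BMAT) at screening, at serological CR and at end of treatment (EOT). The columns for day 1 and day 15 of each cycle, and for day 1 of cycles 3 and 6, are blank in that row.

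**Missing assessments.** Section 7.1.6 divides responders by all registered patients. It says that a patient "whose re-staging information is missing for any reason, will be considered to have not met the primary efficacy endpoint". Section 7.1.4 has the same rule for patients not known to have reached at least PR.

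**The concern.** A marrow-only patient can be scored PR only from a marrow taken on treatment. The schedule's one on-treatment trigger is a serological event, and these patients are defined by having no measurable serological disease. If the marrow is not taken, the non-responder rule turns a gap in ascertainment into a failure on the primary endpoint. The error runs one way: a real marrow response is recorded as none. The stake is a downward bias in ORR and a loss from the stated 0.80 probability of declaring efficacy. Analysis cannot repair it later, because the measurement was never planned.

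**Working it through.** **1. Does any scheduled visit show a marrow PR?**

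| Scheduled marrow | Can it show PR in a marrow-only patient? |
|---|---|
| Screening | No, it is the baseline |
| Serological CR | Only if a detectable serological marker disappears. In a truly non-secretory patient immunofixation is negative from the start, so the trigger is undefined |
| Progression / EOT | Doubtful. The footnotes link both to progression, the visit follows the last dose, and section 3.1 ties response to being on ITD |
| Cycle visits | No marrow scheduled |

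**2. Reproduce the plan's figure.** Inputs from sections 7.1.1 and 7.1.6: n = 45; observed ORR at least 60%; posterior probability that ORR exceeds 45% of at least 90%; prior Beta(0.86805, 1); true ORR 65%.

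- First criterion: 0.60 × 45 = 27 responders.
- Second criterion: with 27 of 45 the posterior is Beta(27.868, 19), and P(ORR > 0.45) = 0.977. At 25 of 45 it is already 0.919, so the first criterion sets the threshold.
- P(Bin(45, 0.65) ≥ 27) = 0.806, against the stated 0.80. The figure reproduces.

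**3. Effect of k patients who cannot be scored.** They stay in the denominator, so 27 responders must come from 45 − k patients. Expected observed ORR is 0.65 × (45 − k)/45, and the probability of declaring efficacy is P(Bin(45 − k, 0.65) ≥ 27).

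| k | Expected observed ORR | Probability of declaring efficacy |
|---|---|---|
| 0 | 65.0% | 0.806 |
| 1 | 63.6% | 0.749 |
| 2 | 62.1% | 0.683 |
| 3 | 60.7% | 0.608 |

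These figures assume that every such patient is a certain failure, so they bound the loss for a given k.

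**4. Averaged over an assumed share s.** The documents give no share. I assume 1% to 5%. The chance of at least one such patient among 45 is 1 − (1 − s)^45, and the averaged probability of success is P(Bin(45, 0.65(1 − s)) ≥ 27).

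| s | Expected number, 45s | Chance of at least one | Probability of declaring efficacy |
|---|---|---|---|
| 1% | 0.45 | 0.36 | 0.780 |
| 2% | 0.90 | 0.60 | 0.751 |
| 5% | 2.25 | 0.90 | 0.657 |

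**The case against.** A reader might infer that a marrow-only patient can never be scored as a responder. The protocol does not support that, for four reasons.

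- Unmeasurable means below the footnote 5 thresholds, not absent. A patient with low but detectable M-protein can lose it and meet the serological part of CR ("Negative immunofixation on the serum and urine and"). That triggers a marrow, which can support CR or a PR by plasma-cell fall.
- The grid marks BMAT at EOT, and one sample is enough, since "Bone marrow assessments need not be confirmed". A patient who stops for toxicity might show the fall there. This route is uncertain: the footnote says "Patients who discontinue the study drug regimen for disease progression must complete the end-of-treatment (EOT) visit" and places no such duty on patients who stop for other reasons.
- Nothing forbids an unscheduled marrow, and section 7.1.4 spares a patient already known to have reached PR.
- In a non-secretory patient the serological-CR trigger is undefined rather than excluded.

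The size also rests on an assumed share. To be affected, a patient must fall below three serological thresholds together and have at least 30% plasma cells. At a 1% share the loss is under three points. The bias is also conservative: the chance of declaring efficacy at a true ORR of 45% falls from 0.031 with no such patient to 0.021 with one, so this cannot produce a false claim of benefit.

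All of this stands and narrows the point. The mismatch remains: the primary endpoint in these patients depends on a chance or unscheduled sample. The per-protocol sensitivity analysis in section 7.1 gives no assured remedy, because its listed deviations do not name this case, although the list is open-ended.

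**Conclusion.** The point holds in limited form. Appendix 11.4, section 5.1 and the Schedule of Events do not fit together for marrow-only disease. Without serological CR, no scheduled on-treatment marrow can show PR, and patients with no detectable serological marker will in practice be counted as failures.

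If each is a certain failure, the first such patient costs about 6 points of the probability of declaring efficacy and the second about 7 more. Averaged over the assumed 1% to 5% share, the loss runs from about 3 to 15 points (0.806 − 0.780 and 0.806 − 0.657). The subgroup may be empty, and the upper end of the range has no support in the documents. The stated 0.80 is correct for patients who can all be assessed. The finding should not be read as an error in the sample-size calculation.

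**What to change.** Make three matching changes; none adds a procedure.

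1. In section 5.1, require disease measurable by at least one of serum M-protein, urine M-protein or FLC, at the thresholds already in footnote 5.
2. In Appendix 11.4, remove the marrow-only entry from footnote 5 and the marrow-only sentence from the Partial Response text. This must go with the first change. Alone, it would leave these patients able to enrol with no route to PR. Equally, a bare reference in 5.1 to measurable disease as Appendix 11.4 now defines it would still admit them.
3. If a marrow-only patient is already registered, keep the Full Analysis Set result as primary and report one sensitivity ORR that excludes patients not assessable by the scheduled measurements.

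The cost is a few lines of text and one extra line of output. The downside is that rare marrow-only patients are no longer eligible. Keeping them eligible would instead require scheduled marrow assessments that do not depend on serological CR, which adds a procedure for those patients. By either route, if all 45 patients can be assessed, the probability of declaring efficacy at a true ORR of 65% is again 0.806.
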